11.2.7. Complaint Handling

Clearside collects product complaints on study drugs and SCS Microinjectors used in clinical studies in order to ensure the safety of study participants, monitor quality, and to facilitate process and product improvements.

All product complaints associated with material packaged, labeled, and released by Clearside will be reported via product complaint forms.

The complainant (the Investigator, site staff, etc.) or his/her designee is responsible for handling the following aspects of the product complaint process in accordance with the instructions provided for this study:

- Recording a complete description of the product complaint reported and any associated AEs using the study-specific complaint forms provided for this purpose.
- Emailing the completed product complaint form within 48 hours to Clearside at the following address: [contact].
- Returning a Study drug/ SCS Microinjector for investigation when directed by Clearside.

12. STATISTICS

A detailed statistical analysis plan will be prepared for this study. The plan will contain a discussion of the statistical methods, a description of the computational algorithms, data handling conventions, and specifications for the data summaries and listings. It will be finalized before the last subject enrolled has completed the study.

The analysis will include all subject data collected in the Parent study and this extension study for all subjects included in the Safety Population (Section 12.4.1). Safety data to be summarized will be limited to the endpoints collected in this extension study.

[figure not shown]
12.1. Randomization

Not applicable.

12.2. Determination of Sample Size and Level of Significance

Sample size is not statistically driven as this is an extension study of Cohorts 2, 3 and 4 of the Parent study, CLS1002-101. In the Parent study, it is planned to enroll a total of approximately 20 to 25 subjects (approximately 5 subjects (Visit 2, Baseline)) in each of the 4 dose cohorts. A maximum of 19 subjects from the Parent study (approximately 5 each in Cohorts 2, 3 and 4) are expected to be eligible to enroll into this extension study.

This is an open-label non-interventional study; therefore, no formal statistical testing of the endpoints will be conducted.

12.3. Subject Disposition and Demographic and Baseline Characteristics

Subject disposition and demographic and baseline characteristics will be summarized descriptively by dose cohort and overall.

12.4. Analysis Populations

12.4.1. Safety Population

The Safety Population will include all subjects who are administered CLS-AX in the Parent study, who have provided informed consent for participating in the Extension study, and from whom at least one safety measurement is obtained after the subject has provided informed consent.

In the safety analysis, all subject data from both the Parent and extension studies will be used; no data will be excluded due to protocol deviations.

All safety analyses will be based on the Safety Population.

12.5. Analysis Methods

Analyses of all safety data will be performed on the Safety Population. All safety outcomes from both the Parent and extension studies will be summarized by dose cohort. Ophthalmic

safety, including ocular adverse events, will be presented for the study eye and separately for the fellow-eye.

Safety endpoints are provided in Section 7.2. Additional endpoints will be described in the statistical analysis plan.

12.5.1. Schedule of Analyses

The study duration will consist of 12 weeks of additional follow-up after the subject has completed participation in the Parent study CLS1002-101.

Analyses of study data for evaluating Cohort 2 will be performed after all subjects enrolled into the dose cohort have completed Visit 8 (Week 24) of the extension (or have been discontinued from the study prior to this visit) and the data has been locked.

Analyses of study data for evaluating Cohort 3 and for comparison between Cohorts 2 and 3 will be performed after all subjects enrolled into Cohort 3 have completed Visit 8 (Week 24) of the extension (or have been discontinued from the study prior to this visit) and the data has been locked.

Analyses of study data for evaluating Cohort 4 and for comparison between all dose cohorts will be performed after all subjects enrolled into Cohort 4 have completed Visit 8 (Week 24) of the extension (or have been discontinued from the study prior to this visit) and the data has been locked.

12.5.2. Safety Analysis

The summary of adverse events (and SAEs) will be limited to TEAEs. Treatment-emergent adverse events are defined as an event that emerges during treatment with CLS-AX (Visit 2, Day 1) having been absent pre-treatment or worsens relative to the pre-treatment state.

For summarizing adverse events, each reported adverse event term will be coded to a preferred term and its corresponding system organ class (SOC) using the Medical Dictionary for Regulatory Activities (MedDRA) coding dictionary. Summary tables will be presented by dose cohort.

Summary tables of TEAEs will be produced for the following categories divided into Study Eye TEAEs, Fellow Eye TEAEs, ocular TEAEs, non-ocular TEAEs and overall TEAEs, grouped by SOC and preferred term:

- All TEAEs.
- All treatment-related TEAEs.
- All TEAEs leading to study discontinuation.
- All SAEs.
- All treatment-related SAEs.
- All TEAEs leading to death.

For each summary, adverse events will be summarized by presenting the number and percentage of subjects reporting each event at least once, and the total number of events reported.

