7.2.1. Primary Endpoint

The primary endpoint for evaluating the continued tolerability of the three dose cohorts will be based on the number of subjects experiencing treatment-emergent (TEAEs), and serious adverse events (SAEs). Treatment-emergent adverse events are defined as an event that emerges following treatment with CLS-AX (administered at Visit 2 (Baseline, Day 1) of the Parent study, CLS1002-101), having been absent pre-treatment or worsens relative to the pre-treatment state.

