11.2.3. Recording Adverse Events

Adverse events spontaneously reported by the subject and/or in response to an open question from the study personnel or revealed by observation will be recorded during the study at the investigational site on the CRF. Information about AEs will be collected from the time of signing of the consent form until 30 days after the end of study participation. Detailed information regarding all SAEs should be collected from the signing of the informed consent until the end of the study. SAEs that are considered related to the use of study drug, SCS

Microinjector, and/or study procedure by the Investigator may be reported by the Investigator if they occur after the end of the study. The Investigator must continue to follow the patient until the SAE has resolved, the condition has become chronic in nature, the condition stabilizes (in the case of persistent impairment), the patient experiences a fatal outcome or is lost to follow up.

The AE term should be reported in standard medical terminology as concisely as possible. In general, the AE recorded should not be a procedure, outcome, or clinical/laboratory measurement, but should reflect the event leading to the procedure, outcome, or the cause of the clinical/laboratory abnormality, if known. Whenever possible, AEs should be evaluated and recorded as a diagnosis, rather than as individual signs or symptoms. However, if a definitive diagnosis is not possible, the individual signs and symptoms should be recorded. For each AE, the Investigator will evaluate and report the onset (date and time), resolution (date and time), intensity, causality, action taken, seriousness, outcome (if applicable), and whether or not it caused the patient to discontinue the study.

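### The TEAE and SAE tables run cumulatively from the Parent Day 1 dose with no split by onset, so they do not separate what began after Parent exit

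*Combined protocol and SAP*

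**What the plan says.** Section 7.2.1 reads: "The primary endpoint for evaluating the continued tolerability of the three dose cohorts will be based on the number of subjects experiencing" TEAEs and SAEs. It defines a TEAE as "an event that emerges following treatment with CLS-AX (administered at Visit 2 (Baseline, Day 1) of the Parent study", so the clock starts at the Parent dose and not at extension entry. Section 12.5.2 words the definition slightly differently (during rather than following treatment) but anchors it at the same visit; I read the two as the same rule.

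The data are pooled. Section 12.4.1 states that "all subject data from both the Parent and extension studies will be used", and Section 12.5 that "All safety outcomes from both the Parent and extension studies will be summarized by dose cohort".

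Section 12.5.2 then sets out the tables. There are six categories: all TEAEs, treatment-related TEAEs, TEAEs leading to discontinuation, SAEs, treatment-related SAEs, and TEAEs leading to death. These are "divided into Study Eye TEAEs, Fellow Eye TEAEs, ocular TEAEs, non-ocular TEAEs and overall TEAEs, grouped by SOC and preferred term". Each table is filled by "presenting the number and percentage of subjects reporting each event at least once, and the total number of events reported". Onset period is not among the divisions.

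The window ends later than Week 24: "Information about AEs will be collected from the time of signing of the consent form until 30 days after the end of study participation" (Section 11.2.3; Section 11.2.4 agrees). Section 11.2.3 also requires the onset date and time of every event.

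**The concern.** The endpoint is framed as continued tolerability. The synopsis gives the study's purpose as continuing to characterize how durable the safety and tolerability of one dose are, and Section 5 justifies longer follow-up partly by a fuller assessment of long-term safety. A reader will therefore look in the AE tables for what happened after the Parent study ended.

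The tables as described do not show it. A count of subjects with at least one event can register each subject once. Whoever had a TEAE in the first 12 weeks, including an event on the injection day, is already in the any-TEAE row. The total number of events does rise with each late event, but without dates it mixes the two periods.

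Section 12.5.1 plans an evaluation of each cohort and comparisons between cohorts. With about 5 subjects per cohort, two cohorts could show the same any-TEAE count and differ entirely in how many subjects had new events after Parent exit.

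**Working it through.** The plan states no event rate, power or precision, so there is no figure of its own to reproduce. The inputs from the documents are about 5 subjects per cohort in three cohorts and a maximum of 19 (Sections 7.3 and 12.2). Event risks are my assumptions.

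**Without any model.** Let *a* be the subjects in a cohort of *n* with a Parent-period TEAE and *e* those with a TEAE starting after Parent exit. The cumulative any-TEAE count lies between max(*a*, *e*) and min(*n*, *a* + *e*). Take *n* = 5 and *a* = 4:

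- *e* = 0: the count is 4 of 5.
- *e* = 4, the same four subjects: the count is still 4 of 5.
- *e* = 4, including the fifth subject: the count is 5 of 5.

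Whatever happens after Parent exit, the count can only be 4 or 5.

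**With assumed risks.** Let *p1* be the Parent-period risk of any TEAE and *p2* the later risk, independent within a subject.

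- Expected subjects with a late TEAE: *n* × *p2*.
- Of these, new to the any-TEAE count: *n* × (1 − *p1*) × *p2*.
- Share that leaves the count unchanged: 1 − (1 − *p1*) = *p1*.

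For *n* = 15 (3 × 5), *p1* = 0.6 and *p2* = 0.4, 15 × 0.4 = 6.0 subjects are expected to have a late TEAE, and 15 × 0.4 × 0.4 = 2.4 of them change the count. As a check, the cumulative risk is 1 − 0.4 × 0.6 = 0.76, and 15 × 0.76 − 15 × 0.6 = 11.4 − 9.0 = 2.4.

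With *p2* = 0.4, a split table would be expected to show 2.0 subjects with a late TEAE for *n* = 5, 6.0 for *n* = 15 and 7.6 for *n* = 19. The cumulative count rises by:

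| *p1* | *n* = 5 | *n* = 15 | *n* = 19 | All 5 of a cohort already counted (*p1*⁵) |
|---|---|---|---|---|
| 0.2 | 1.6 | 4.8 | 6.1 | <0.1% |
| 0.4 | 1.2 | 3.6 | 4.6 | 1.0% |
| 0.6 | 0.8 | 2.4 | 3.0 | 7.8% |
| 0.8 | 0.4 | 1.2 | 1.5 | 32.8% |

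If the same subjects tend to have events in both periods, the hidden share is larger than *p1*; with negative dependence it is smaller.

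**Which rows are affected.** The limit applies to the any-TEAE row, to SOC-level subject counts, and to a preferred term that recurs in the same subject. Recurrence is plausible: Section 11.2.1.1 gives a transient IOP rise as an example of an AE related to injection volume, Section 9.4.1 allows intravitreal injections at Visits 6 and 7, and Section 11.1.3 measures IOP after them. The limit does not apply to a preferred term new to the subject, nor to a first SAE in a subject whose earlier events were not serious; each adds to its own row.

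**The case against.** The strongest reply is that the cumulative count is what the primary objective asks for. Section 6.1 sets the horizon at up to 24 weeks after the Parent dose, and Section 7.2.1 starts the TEAE window there on purpose. That stands. A reader might infer that the primary objective goes unanswered or that the primary endpoint is wrong; the documents do not support this. The gap is against the aim of showing continued and durable tolerability.

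Second, a reader might infer that a late safety signal would leave the results unchanged. That is too strong. The tables go down to preferred term, have separate SAE and treatment-related versions, and carry event totals, so a new kind of late event would appear. What they would not show is that it was late.

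Third, one might say that the AE result mainly repeats the Parent study's report, or that late adverse events are the reason for the extension. The documents contain no Parent AE results, and Section 5 argues first from durability of effect on visual acuity and retinal thickness. Neither statement can be made.

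Fourth, Section 12 announces a detailed statistical analysis plan that will specify summaries and listings, and it is not part of the text reviewed. It could add the split, and with at most 19 subjects the timing could be recovered from the data. Both are fair. But Section 12.5.2 already states a concrete table rule, so the split is better written there and carried into that plan than left to chance. Ocular measurements at Visits 6 to 8 describe that period but do not replace dated AE counts.

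**Conclusion.** The point holds in a limited form. The TEAE and SAE tables in Section 12.5.2 are cumulative from the Parent dose and are never divided by onset, so they cannot isolate events that began after Parent exit. The any-TEAE subject count, SOC-level counts and repeated preferred terms cannot register a late event in a subject already counted.

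The certain part needs no assumption: in a cohort of 5 with 4 subjects already counted, the any-TEAE count is 4 or 5 whatever follows. The hidden share of 20% to 80% rests on assumed Parent-period risks of 0.2 to 0.8 and on independence, and is illustrative only. It is smaller for SAEs and single preferred terms if their Parent-period risk is low.

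No stated number is wrong and no test is affected, since the study is descriptive. That the tables cover a single period is read from the absence of any split in the protocol. This is a worthwhile, nearly free improvement in reporting.

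**What to change.** In Section 12.5.2, and in the statistical analysis plan, keep the cumulative counts. For each listed category and dose cohort add the number and percentage of subjects, and the number of events, by onset:

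- (a) from CLS-AX administration to Parent exit;
- (b) after Parent exit to the end of AE collection, 30 days after the end of participation.

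Use Parent exit as the only boundary. Extension consent may be signed before, at or up to 48 hours after Parent Visit 5, and Enrollment Day may fall up to 48 hours after exit, so starting (b) at either could leave a gap or an overlap. Ending (b) at Visit 8 would drop the last 30 days of collected events.

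State that a subject may count in both periods. Use the Safety Population as denominator throughout; Section 12.4.1 already limits it to subjects who consented to the extension. The designation of the primary endpoint need not change. While editing, align the TEAE wording in Sections 7.2.1 and 12.5.2.

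The cost is a few columns per table. Onset date and time are already collected, so no new data, visits or subjects are needed. Rules for partial dates are already assigned to the statistical analysis plan (Section 12.5.8) and should also say how an event is placed when its date could fall on either side of Parent exit.

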12.5.3. Secondary Safety Analyses

Secondary safety analyses will be performed on all subjects in the Safety Population. Ocular safety will be assessed by evaluating IOP, BCVA and outcomes obtained from the slit-lamp biomicroscopy, indirect ophthalmoscopy, SD-OCT, fundus photography and angiography examinations. Summaries will be provided for each dose cohort for the Study eye.

Systemic safety will be assessed by evaluating vital signs and concomitant medications. Summaries will be provided for each dose cohort.

12.5.4. Subgroup Analysis

No subgroup analyses are planned.

12.5.5. Interim Analysis

Analysis of all safety data will be performed at the completion of each dose cohort. No formal statistical testing will be conducted. All inferential statistics will be for descriptive purposes only; therefore, no adjustments will be made to the type 1 error rate to account for multiple analyses of the data.

12.5.6. Pharmacodynamic Analysis

Not applicable.

12.5.7. Pharmacokinetic Analysis

Not applicable.

12.5.8. Procedure for Accounting for Missing Data

Any missing, unused, or spurious data will be noted in the final clinical study report.

No imputation for missing data will be used in the Safety Populations.

Algorithms for handling partial or incomplete dates for adverse events, concomitant medications, and diagnoses will be defined in the statistical analysis plan.

13. DIRECT ACCESS TO SOURCE DATA/DOCUMENTS

13.1. Study Monitoring

During the study, a monitor from Clearside Biomedical, Inc. or representative will have regular contacts (oral, written, onsite, virtual) with the investigational site, for the following:

- Provide information and support to the Investigator (s).
- Confirm that facilities and personnel continue to remain acceptable.
- Confirm that the investigational team is adhering to applicable standards for conducting trials (e.g., ICH, GCP) the protocol, that data are being accurately recorded in the case report forms.
- Perform source data verification. This includes a comparison of the data in the case report forms with the subject's medical records at the hospital or practice, and other source documents relevant to the study. This will require direct access to all original records for each patient (e.g., clinic charts).
- Record and report any protocol deviations not previously recorded in the CRF or reported to IRB and/or Clearside Biomedical, Inc. or designee.
- Confirm AEs and SAEs have been properly documented on CRFs and confirm any SAEs have been forwarded to Clearside Biomedical, Inc, or designee, and those SAEs that met criteria for reporting have been forwarded to the IRB/IEC.

The monitor will be available between visits if the Investigator(s) or other staff needs information or advice.

13.2. Audits and Inspections

Authorized representatives of Clearside Biomedical, Inc, a regulatory authority, an Independent Ethics Committee, or an Institutional Review Board may visit the site to perform audits or inspections, including source data verification. The purpose of a Clearside Biomedical, Inc audit or inspection is to systematically and independently examine all study-related activities and documents to determine whether these activities were conducted, and data were recorded, analyzed, and accurately reported according to the protocol, Good Clinical Practice guidelines of the International Conference on Harmonization, and any applicable regulatory requirements. The Investigator should contact Clearside Biomedical, Inc immediately if contacted by a regulatory agency about an inspection.

13.3. Institutional Review Board (IRB)

The Principal Investigator must obtain IRB/IEC approval for the investigation. Initial IRB/IEC approval, and all materials approved by the IRB/IEC for this study including the subject consent form and recruitment materials must be maintained by the Investigator and made available for inspection.

14. QUALITY CONTROL AND QUALITY ASSURANCE

During study conduct, Clearside or its agent(s) or designee(s) will conduct periodic monitoring visits to ensure the protocol and Good Clinical Practice (GCPs) are being followed. The progress of the study will also be monitored by written, e-mail, and telephone communications between personnel at the study site and the Sponsor and its agent(s) or designee(s). The Investigator will allow Sponsor monitors, or designee(s), direct access to inspect all CRFs, subject records (source documents), signed Informed Consent Forms, study records, and regulatory files related to the study to perform verification and to confirm that the data recorded on CRFs is accurate.

The study site may be subject to review by the Institutional Review Board (IRB)/Independent Ethics Committee (IEC), and/or to quality assurance audits performed by Clearside, or companies working with or on behalf of Clearside, and/or to inspection by appropriate regulatory authorities.

It is important that the Investigator(s) and their relevant personnel are available during the monitoring visits and possible audits, or inspections and that sufficient time is devoted to the process.

15. ETHICS

15.1. Ethics Review

The final study protocol, including the final version of the Informed Consent Form, and other relevant documents, e.g., recruitment advertisements, if applicable, must be approved or given a favorable opinion in writing by an IRB or IEC, as appropriate. The Investigator must submit written approval to Clearside Biomedical, Inc, or designee, before he or she can enroll any subject into the study.

The Principal Investigator is responsible for informing the IRB or IEC of any amendment to the protocol in accordance with local requirements. In addition, the IRB or IEC must approve all advertising used to recruit patients for the study. The protocol must be re-approved by the IRB or IEC upon receipt of amendments and annually, as local regulations require.

The Principal Investigator is also responsible for providing the IRB with reports of any reportable serious adverse drug reactions from any other study conducted with the study drug. Clearside Biomedical, Inc will provide this information to the Principal Investigator.

Progress reports and notifications of serious adverse drug reactions will be provided to the IRB or IEC according to local regulations and guidelines.

All correspondence with the IRB/IEC should be retained in the Investigator File.

15.2. Ethical Conduct of the Study

The study will be performed in accordance with ethical principles that have their origin in the Declaration of Helsinki and are consistent with ICH/GCP, applicable local regulatory requirements and laws. In addition, the study will be conducted in accordance with the protocol.

The Investigator will inform Clearside and/or its agent(s) immediately of any urgent safety measures taken by the Investigator to protect the study subjects against any immediate hazard, and of any serious breaches of this protocol or of ICH GCP that the Investigator becomes aware of.

